10.4.5 Adherence and Retention Analyses

Adherence to the study protocol will be assessed via audits by the principal investigator. Measure of participation and study retention will be assessed when collecting data and reviewing study participants medical records to see if study agent was administered as scheduled based on the study protocol. Any participants with adverse events or any other reasons leading to early withdrawal or termination from the study will be discounted from the study.

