5.2 Exclusion Criteria

An individual who meets any of the following criteria will be excluded from participation in this study:

1. Admitted to the pediatric intensive care unit
2. Has an underlying pre-existing condition that may affect the respiratory system (includes bronchopulmonary dysplasia, reactive airways disease, asthma, restrictive lung diseases, other chronic lung diseases, etc.)
3. Has other comorbid conditions upon admission that may affect the respiratory system (includes pneumonia or other bacterial or fungal lung infections, acute exacerbation of reactive airways disease, acute exacerbation of asthma, pulmonary edema, pleural effusion, etc.)
4. Has an absolute contraindication to nebulized 3% hypertonic saline, for example, a history of an allergic or anaphylactic reaction
5. Is receiving other respiratory treatments such as bronchodilator treatments (i.e. albuterol or levalbuterol)
6. Is receiving other adjuvant therapy such as antibiotics, antivirals, glucocorticoids, corticosteroids, or diuretics

A potential study subject in the control arm via retrospective chart review who meets any of the following criteria will be excluded from this study:

1. Admitted to the pediatric intensive care unit
2. Has an underlying pre-existing condition that may affect the respiratory system (includes bronchopulmonary dysplasia, reactive airways disease, asthma, restrictive lung diseases, other chronic lung diseases, etc.)
3. Has other comorbid conditions upon admission that may affect the respiratory system (includes pneumonia or other bacterial or fungal lung infections, acute exacerbation of reactive airways disease, acute exacerbation of asthma, pulmonary edema, pleural effusion, etc.)
4. Has an absolute contraindication to nebulized 3% hypertonic saline, for example, a history of an allergic or anaphylactic reaction
5. Is receiving other respiratory treatments such as bronchodilator treatments (i.e. albuterol or levalbuterol)
6. Is receiving other adjuvant therapy such as antibiotics, antivirals, glucocorticoids, corticosteroids, or diuretics

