5.7 Participant Withdrawal or Termination

5.7.1 Reasons for Withdrawal or Termination

Participants are free to withdraw from participation in the study at any time upon request. An investigator may terminate participation in the study if:

- Any clinical adverse event (AE), laboratory abnormality, or other medical condition or situation occurs such that continued participation in the study would not be in the best interest of the participant

- The participant meets an exclusion criterion (either newly developed or not previously recognized) that precludes further study participation

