5.7.2 Handling of Participant Withdrawals or Termination

There is no follow up period required in this study after patients are discharged from the general inpatient pediatrics unit and participation in the study has been completed. Participants may choose to withdraw from the study at any time and no information prior to or after withdrawal will be collected from this participant to be utilized in this clinical study. Upon participant withdrawal or termination, every effort will be made to undertake protocol-specific safety follow up procedures to capture adverse events, serious adverse events, and unanticipated problems. Given the safe profile of the medication (nebulized 3% hypertonic saline) and device (chest percussion cup) used, there is no anticipated risk of adverse events or serious adverse events.

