10.3 Analysis Datasets

Control group: Patients meeting criteria as above prior to start date, beginning 12 months prior to start date of study, will be examined via retrospective chart review.

Experimental group: All patients meeting criteria as above beginning start date of study will be enrolled in study to receive adjuvant therapy with 3% hypertonic saline nebulization treatments combined with 3 minutes of chest physiotherapy.

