10.6 Measures to Minimize Bias

This study is not blinded. All patients who meet the inclusion criteria are eligible to enroll in the study and would be receiving the investigational therapy of nebulized 3% hypertonic saline combined with chest percussion therapy. These participants will be part of the experimental arm of the study. No masking or randomization is required. It is expected that at least 114 subjects in this group will be required to accommodate for a type I error of 0.05 and a power of 0.80. An estimate of approximately 200 participants will be required to be enrolled in this study to account for early withdrawal from the study for any reason.

11 Source Documents and Access to Source Data/Documents

Source data is all information, original records of clinical findings, observations, or other activities in a clinical trial necessary for the reconstruction and evaluation of the trial. Source data are contained in source documents. Examples of these original documents, and data records include: hospital records, clinical and office charts, laboratory notes, memoranda, subjects' diaries or evaluation checklists, pharmacy dispensing records, recorded data from automated instruments, copies or transcriptions certified after verification as being accurate and complete, microfiches, photographic negatives, microfilm or magnetic media, x-rays, subject files, and records kept at the pharmacy, at the laboratories, and at medico-technical departments involved in the clinical trial. It is acceptable to use CRFs as source documents. If this is the case, it should be stated in this section what data will be collected on CRFs and what data will be collected from other sources.

The study case report form (CRF) is the primary data collection instrument for the study. All data requested on the CRF must be recorded. All missing data must be explained. If a space on the CRF is left blank because the

procedure was not done or the question was not asked, write "N/D". If the item is not applicable to the individual case, write "N/A". All entries should be printed legibly in black ink. If any entry error has been made, to correct such an error, draw a single straight line through the incorrect entry and enter the correct data above it. All such changes must be initialed and dated. DO NOT ERASE OR WHITE OUT ERRORS. For clarification of illegible or uncertain entries, print the clarification above the item, then initial and date it.

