13.4 Participant and Data Confidentiality

Information about study subjects will be kept confidential and managed according to the requirements of the Health Insurance Portability and Accountability Act of 1996 (HIPAA). Those regulations require a signed subject authorization informing the subject of the following:

- What protected health information (PHI) will be collected from subjects in this study
- Who will have access to that information and why
- Who will use or disclose that information
- The rights of a research subject to revoke their authorization for use of their PHI.

In the event that a subject revokes authorization to collect or use PHI, the investigator, by regulation, retains the ability to use all information collected prior to the revocation of subject authorization. For subjects that have revoked authorization to collect or use PHI, attempts should be made to obtain permission to collect at least vital status (i.e. that the subject is alive) at the end of their scheduled study period.

Participant confidentiality is strictly held in trust. This confidentiality is extended to cover the clinical information relating to participants. Therefore, the study protocol, documentation, data, and all other information generated will be held in strict confidence. No information concerning the study or the data will be released to any unauthorized third party without prior written approval of the sponsor.

The study monitor, other authorized representatives of the sponsor, representatives of the IRB or pharmaceutical company supplying study product may inspect all documents and records required to be maintained by the investigator, including but not limited to, medical records (office, clinic, or hospital) and pharmacy records for the participants in this study. The clinical study site will permit access to such records.

The study participant's contact information will be securely stored at each clinical site for internal use during the study. At the end of the study, all records will continue to be kept in a secure location for as long a period as dictated by local IRB and Institutional regulations.

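### Removing everyone who stops early, with no all-enrolled analysis set, selects on post-enrolment events at least partly in one arm and probably favours the treatment

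*Combined protocol and SAP*

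**What the plan says.** Section 10.4.5 (Adherence and Retention Analyses) ends with the rule: "Any participants with adverse events or any other reasons leading to early withdrawal or termination from the study will be discounted from the study". Section 5.7.2 points the same way: after a participant chooses to withdraw, "no information prior to or after withdrawal will be collected from this participant to be utilized in this clinical study".

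Section 5.7.1 says an investigator may terminate participation for an adverse event or other medical condition. It gives a second ground: "The participant meets an exclusion criterion (either newly developed or not previously recognized) that precludes further study participation". The exclusion criteria in section 5.2 include intensive care admission, bronchodilators, antibiotics and corticosteroids, and the same six criteria are listed for the control charts.

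Section 10.3 (Analysis Datasets) says who belongs to each group but not how early leavers are analysed. The control group is historical: "Patients meeting criteria as above prior to start date, beginning 12 months prior to start date of study, will be examined via retrospective chart review". Section 10.4.4 lists adverse events that lead to discontinuation, but this does not return those children to the efficacy comparison.

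On numbers, section 10.6 says "approximately 200 participants will be required to be enrolled in this study to account for early withdrawal", and section 5.6 expects about 200 enrolled to give 114 evaluable. Section 5.4 says about 200 will be screened, and section 5.6 also ends recruitment at about 114 enrolled.

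**The concern.** Whether a child stops early is decided after treatment has begun, and several of the listed grounds are signs that the child is doing badly. If those children leave the analysis, the experimental group drifts towards children who tolerated treatment and did not deteriorate. A control chart has no consent to withdraw and no study-treatment adverse event to be terminated for, so at least part of this filter has no counterpart.

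Both primary endpoints are exposed. The design is open and non-randomised, so nothing else in it would offset the selection. An ineffective treatment could appear to shorten stay and time on oxygen.

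**Working it through.** **Inputs from section 10.5.** Mean stay 6.5 days, SD 3.5 days, a 20% decrease to detect (0.20 × 6.5 = 1.3 days), type I error 0.05, power 0.80. Sidedness is not stated; two-sided is assumed.

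**The plan's own figure.** n per group = 2 × (1.960 + 0.842)² × 3.5² / 1.3² = 113.8, so 114 per group and 228 in total, as stated. Power at 114 is 0.801. A one-sided test would need 90, so two-sided is the reading that fits. The nominal chance of a false claim of benefit is therefore 2.5%.

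**Bias without a model.** Let w be the share removed from the experimental arm and D the mean excess stay of removed over retained children. With no true effect, the retained mean falls below the full mean by w × D. All values of D are assumptions, and so is w.

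- w = 10%, D = 2: 0.20 day; false benefit 6.3%
- w = 20%, D = 2: 0.40 day; 13.6%
- w = 43%, D = 1: 0.43 day; 15.1%
- w = 43%, D = 2: 0.86 day; 45.8%

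**Bias with a model.** Assume lognormal stay with σ = √ln(1 + (3.5/6.5)²) = 0.505. Remove the top fraction f of a latent score that has correlation ρ with log stay. The spurious reduction is

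6.5 × [1 − Φ(z − ρσ)/(1 − f)], with z = Φ⁻¹(1 − f).

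Example, f = 20% and ρ = 0.3: z = 0.842, ρσ = 0.151, Φ(0.690) = 0.755, 0.755/0.80 = 0.944, and 6.5 × 0.056 = 0.37 day.

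The false-benefit rates come from simulation: 114 retained against 114 controls, two-sample t-test, at least 10,000 runs per scenario. Ranges show variation between runs.

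| Removed | ρ = 0.1 | ρ = 0.3 | ρ = 0.5 |
|---|---|---|---|
| 10% | 0.07 day; 3–4% | 0.21 day; 7% | 0.37 day; 13–14% |
| 20% | 0.12 day; 4% | 0.37 day; 13% | 0.63 day; 30–31% |
| 43% | 0.23 day; 7% | 0.68 day; 35% | 1.14 days; 80–81% |

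The 43% row is (200 − 114)/200. It applies only if 200 means enrolled.

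**Checks in the other direction.**

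- *Removal unrelated to stay:* no bias, and false benefit stays near 2.5%.
- *Removed children have shorter stays:* the bias reverses. With gamma-distributed stay and odds of removal falling 1.25-fold per day, the experimental mean rises by 0.20 day at 10% removed and 0.96 day at 43%.
- *Few removals:* at 2% removed and ρ = 0.3 the formula gives 0.06 day, with false benefit about 3%. The adverse-event rates quoted in section 2.4.1 are 0.3% for bronchospasm and 1.0% for other events.
- *Controls lose half the share by the same mechanism, ρ = 0.3:* false benefit is about 4%, 5% and 11% at 10%, 20% and 43% removed.

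**The case against.** Four stronger readings are tempting, and the documents support none of them fully.

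- *That a child who goes to intensive care or receives a bronchodilator must drop out of the analysis.* Section 5.7.1 says the investigator may terminate. Removal is possible, not automatic. Once a child is terminated, though, section 10.4.5 applies without discretion.
- *That the comparison is with unfiltered control charts.* Section 5.2 applies the same exclusions to controls. If these are read over the whole stay, the new-exclusion route is partly mirrored; the documents do not say whether later events count. Adverse-event and voluntary withdrawal still have no counterpart.
- *That the plan expects to lose 43%.* Sections 5.6 and 10.6 support this, but section 5.4 says 200 screened and section 5.6 also ends recruitment at about 114 enrolled. The figure is conditional on one side of an unresolved conflict.
- *That section 13.4 contradicts section 5.7.2.* Section 13.4 says that after revocation the investigator "retains the ability to use all information collected prior to the revocation of subject authorization". That is a permission, and declining to use it is compatible. The tension between section 5.7.2 and section 7.3.5, which collects vital signs, oxygen settings and surveys at withdrawal, is real but partial, because section 5.7.2 itself keeps safety follow-up.

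It is also fair to say that the correlations have no source in the documents and that families may withdraw for reasons unrelated to the child's course. This limits what can be said about size and makes the direction an inference. It does not supply an analysis that includes the children who stop.

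**Conclusion.** The concern holds. The removal rule is explicit, section 5.7.2 reinforces it, and nothing in the plan brings early leavers back into the efficacy comparison. The selection is at least partly confined to the experimental arm. Bias towards benefit is the more probable direction, because the named grounds for termination tend to accompany a worse course and a longer stay gives more time in which to stop.

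The size cannot be fixed from the documents. It runs from negligible, with a few per cent removed or a weak link to stay, to about half of the 1.3-day target at 20% removed and correlation 0.5 (0.63/1.3 = 49%). It is larger still only if 43% are really removed. A reader might infer that a positive result would be an artefact. That goes too far, since neither the share removed nor its relation to stay is known. What can be said is that the plan as written could not separate a treatment effect from this selection. It should be changed before any data are analysed.

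**What to change.** Replace the last sentence of section 10.4.5 with a defined primary analysis set: all consented participants who start study treatment are analysed in the experimental group whether or not treatment stops. Take length of stay and oxygen time from the hospital record through hospital discharge, defined identically in both arms. In addition:

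- Distinguish stopping study treatment (outcome data kept) from withdrawal of permission (data collected before revocation kept, as section 13.4 permits). Reconcile section 5.7.2 with sections 7.3.5 and 13.4.
- For the analysis set, apply the section 5.2 exclusions in both arms by status at the same time zero (admission), not by later events.
- Report numbers and reasons for stopping, and keep the completers analysis as a labelled sensitivity analysis.
- Reconcile sections 5.4, 5.6 and 10.6 on whether 200 is screened or enrolled.

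This concerns analysis only; it does not alter when a child's treatment is stopped.

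The cost is mostly wording, since the outcomes are in the hospital record. The Protocol Summary and section 5.5 end participation at discharge from the general unit, so these and any matching consent text need aligning. The estimated effect may also be smaller. With 200 experimental and 114 control children, power is 0.886 if the full 1.3 days holds in everyone. If children who stop gain nothing (an assumption) and enrolment is raised to keep 114 completers, the effect is 1.3 × (1 − w) and power is 0.735, 0.657 and 0.438 at 10%, 20% and 43% stopping. The sample size should be reviewed with that in mind.

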10.4.6 Baseline Descriptive Statistics

Baseline descriptive statistics will include participant age and gender.

10.4.7 Planned Interim Analysis

Not applicable.

10.4.7.1 Safety Review

Study enrollment will cease upon participant/participant's caregiver's voluntary request to do so or should a serious adverse event occur. No statistical rules will be used for safety review.

10.4.7.2 Efficacy Review

Descriptive statistics (mean \pm standard deviation or median [25th, 75th percentiles] for continuous variables; frequencies and percentages for categorical variables) will be calculated separately by group. The two groups will be compared using the chi-square test or Fisher's exact test, as deemed appropriate, for categorical variables and the two-sample t-test or Mann-Whitney test for continuous data.

For all analyses, the standard assumptions of Gaussian residuals and quality of variance will be tested. If the standard assumptions are not met, a transformation will be performed (i.e. logarithm transformation). Results will be brought back to the original units and reported as geometric means with their corresponding lower and upper confidence limits.

For the assessment of number of days on supplemental oxygen therapy (i.e. count data), a Poisson, Negative Binomial (NB), Zero-Inflated Poisson (ZIP), or Zero-Inflated Negative Binomial (ZINB) model will be used.

A result will be considered statistically significant at the $p < 0.05$ level of significance. All analyses will be performed using SAS version 9.4 (SAS Institute Inc., Cary, NC). The proposed sample size for this study is 228 subjects ($n=114$ per group). The mean duration of hospitalization for bronchiolitis recorded in the study hospitals during previous years was 6.5 days and standard deviation of 3.5 days. For a type I error of 0.05 and a power of 0.80, for detecting a 20% decrease in duration of hospitalization, a total of 228 subjects would be included (114 subjects in each group).

10.4.8 Tabulation of Individual Response Data

Individual participant data will be listed by primary and secondary outcomes measures and respective time points.

10.5 Sample Size

The proposed sample size for this study is 228 subjects ($n=114$ per group). Based on data published by Gajdos, et al., the mean duration of hospitalization for bronchiolitis recorded in the study hospitals during previous years was 6.5 days and standard deviation = 3.5 days. For a type I error of 0.05 and a power of 0.80, for detecting a 20% decrease in duration of hospitalization, a total of 228 subjects would be included (114 subjects in each group).

10.6 Measures to Minimize Bias

This study is not blinded. All patients who meet the inclusion criteria are eligible to enroll in the study and would be receiving the investigational therapy of nebulized 3% hypertonic saline combined with chest percussion therapy. These participants will be part of the experimental arm of the study. No masking or randomization is required. It is expected that at least 114 subjects in this group will be required to accommodate for a type I error of 0.05 and a power of 0.80. An estimate of approximately 200 participants will be required to be enrolled in this study to account for early withdrawal from the study for any reason.

11 Source Documents and Access to Source Data/Documents

Source data is all information, original records of clinical findings, observations, or other activities in a clinical trial necessary for the reconstruction and evaluation of the trial. Source data are contained in source documents. Examples of these original documents, and data records include: hospital records, clinical and office charts, laboratory notes, memoranda, subjects' diaries or evaluation checklists, pharmacy dispensing records, recorded data from automated instruments, copies or transcriptions certified after verification as being accurate and complete, microfiches, photographic negatives, microfilm or magnetic media, x-rays, subject files, and records kept at the pharmacy, at the laboratories, and at medico-technical departments involved in the clinical trial. It is acceptable to use CRFs as source documents. If this is the case, it should be stated in this section what data will be collected on CRFs and what data will be collected from other sources.

The study case report form (CRF) is the primary data collection instrument for the study. All data requested on the CRF must be recorded. All missing data must be explained. If a space on the CRF is left blank because the

procedure was not done or the question was not asked, write "N/D". If the item is not applicable to the individual case, write "N/A". All entries should be printed legibly in black ink. If any entry error has been made, to correct such an error, draw a single straight line through the incorrect entry and enter the correct data above it. All such changes must be initialed and dated. DO NOT ERASE OR WHITE OUT ERRORS. For clarification of illegible or uncertain entries, print the clarification above the item, then initial and date it.

Access to study records will be limited to IRB-approved members of the study team. The investigator will permit study-related monitoring, audits, and inspections by the IRB/EC, the sponsor, government regulatory bodies, and University compliance and quality assurance groups of all study related documents (e.g. source documents, regulatory documents, data collection instruments, study data etc.). The investigator will ensure the capability for inspections of applicable study-related facilities (e.g. pharmacy, diagnostic laboratory, etc.).

Participation as an investigator in this study implies acceptance of potential inspection by government regulatory authorities and applicable University compliance and quality assurance offices.

12 Quality Assurance and Quality Control

QC procedures will be implemented beginning with the data entry system and data QC checks that will be run on the database will be generated. Any missing data or data anomalies will be communicated to the site(s) for clarification/resolution.

Following written SOPs, the monitors will verify that the clinical trial is conducted and data are generated, documented (recorded), and reported in compliance with the protocol, GCP, and the applicable regulatory requirements (e.g., Good Laboratory Practices (GLP), Good Manufacturing Practices (GMP)).

The investigational site will provide direct access to all trial related sites, source data/documents, and reports for the purpose of monitoring and auditing by the sponsor, and inspection by local and regulatory authorities.

13 Ethics/Protection of Human Subjects

